7.3 LOST TO FOLLOW-UP

A participant will be considered lost to follow-up if they fail to attend scheduled visits and cannot be contacted after three attempts (via telephone at different times of day).

To minimize loss to follow-up, the following measures will be implemented:

- Sending reminders prior to each scheduled visit.
- Rescheduling missed visits.
- Recording all contact attempts.

If these measures are unsuccessful and contact with the participant cannot be established, the participant will be classified as "lost to follow-up" and will be excluded from the intervention.

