- **SF-36:** This is a generic scale that provides a health status profile and is applicable both to patients and to the general population. The 36 items of the instrument cover the following domains: Physical Functioning, Role Physical, Bodily Pain, General Health, Vitality, Social Functioning, Role Emotional, and Mental Health. For each domain, items are coded, aggregated, and transformed into a scale ranging from 0 (worst health status for that dimension) to 100 (best health status) (*Alonso et al., 1995*).

e) Medication consumption

- **Defined Daily Dose (DDD) by active substance:** DDDs of the active substances consumed will be classified according to ATC7. Each ATC classification has a defined daily dose based on international standards, which determine the recommended maximum daily amount for the approved indication of the active substance (*WHOCC, n.d.*).

Control variables and management of T2DM

Patients will be assessed during each follow-up telephone visit throughout the intervention, at the end of the intervention, and one year after its completion. For the control group (Group B), episodes will be identified through records in the electronic health record system (eCAP).

- **Number of hypoglycemia episodes:** Episodes of hypoglycemia detected by patients through capillary blood glucose levels and/or recorded in eCAP during the intervention (plasma glucose <60 mg/dl).
- **Number of symptomatic hyperglycemia episodes:** Episodes of hyperglycemia recorded in eCAP during the intervention (plasma glucose >350 mg/dl accompanied by compatible symptoms such as general malaise, nausea, asthenia, among others).

- **Total number of healthcare visits:** Annual contacts with the healthcare system including Primary Care (physicians and nursing), Specialized Care, and Emergency Care.
- **Number of diabetes-related emergency episodes:** Emergency visits related to diabetes during the intervention period.

Recruitment

Through the internal registry of the Primary Care Clinical Station (eCAP), patients with a diagnosis of Type 2 Diabetes Mellitus (T2DM) from each primary care center (CAP) will be identified. Potential participants will be validated by a physician not involved in the intervention, in order to exclude false positives due to registry errors and to confirm inclusion and exclusion criteria.

Randomization will be performed by stratifying according to the characteristics defined in section 6.2. Study Design.

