Potential participants will receive an invitation to take part in the study during their last medical consultation (in person or by telephone) by their physician, nurse, or the principal investigator. They will then be scheduled for a screening visit with a member of the research team, following completion of the screening blood test. Patients will be informed of the necessary requirements for the laboratory tests (fasting status and first morning urine sample) as well as the location where they will be carried out (extraction and laboratory areas of each primary care center).

Screening and Study Inclusion Visit

During this visit, eligibility criteria will be assessed to determine whether patients meet the study selection requirements. Participants who fulfill the criteria will receive a detailed explanation of the study objectives and the implications of participation. They will be provided with the study information sheet and, if they agree to participate, will sign an informed consent form for data collection throughout the study. If consent is obtained, a physical examination (anthropometric measurements) will be performed, sociodemographic variables will be recorded, and participants will complete the questionnaires assessing quality of life, physical activity, nutritional status, and lifestyle habits (including substance use). Additionally, appointments will be scheduled for all participants to undergo the imaging test (Carotid ultrasonography).

Laboratory Tests

Blood and urine analyses will be performed at three different time points during the study: at baseline, at the end of the intervention, and 12 months after completion of the intervention. These analyses do not involve any additional procedures, as they are part of the routine clinical practice for monitoring and follow-up of all patients with type 2 diabetes mellitus (T2DM) in primary care. No requests, extractions, or analyses will be conducted outside of standard clinical care. The laboratory tests will include: Complete blood count, HbA1c, Creatinine, Glomerular filtration rate, GOT (AST), GPT (ALT), GGT, Ionogram, Lipid profile (Total cholesterol, HDL, LDL,

Triglycerides, Apo B100), Fasting insulin, Anti-GAD antibodies (only at baseline), Urine: sediment and albumin/creatinine ratio.

Imaging Diagnosis: Carotid ultrasonography

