9.2 SAMPLE SIZE DETERMINATION

Based on the primary variable of the intervention, the percentage of T2DM remission, the required sample size has been calculated to observe statistically significant differences. This variable will be coded dichotomously. A total of 120 volunteers (60 per arm) will be recruited for the study. Accepting an alpha risk of 0.05 (5%) and a beta risk of less than 0.2 in a two-sided test, at least 52 subjects in the control group and 52 subjects in the intervention group would be required to detect as statistically significant a 20% difference between two proportions (primary endpoint: T2DM remission). For the control group, the expected remission rate ranges from 0 to 5%, whereas in the intervention group, it is expected to be at least 25%. The remission rates have been benchmarked against previous studies (Lean et al., n.d.). An estimated loss to follow-up rate of 15% has been considered.

Given the estimated 15% loss to follow-up, the sample size has been increased to 60 participants instead of 52. This ensures that the statistical power of the analysis will be preserved.

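### Sections 7.2 and 7.3 give no rule for taking the 6- and 18-month outcome from routine records when a participant is lost, although the study bloods are routine care and the trial already reads eCAP

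*Protocol*

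**What the plan says.** **Loss to follow-up.** Section 7.3 sets a joint condition: "A participant will be considered lost to follow-up if they fail to attend scheduled visits and cannot be contacted after three attempts". The steps meant to prevent this are reminders, a log of contact attempts and "Rescheduling missed visits". If they fail, the participant is classified as lost and "will be excluded from the intervention". Section 7.2 lists loss of contact as a ground for permanent discontinuation. Neither section mentions obtaining the outcome by another route. Section 5.5 says there is no specific retention plan.

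**Analysis.** Section 9.2 assumes: "An estimated loss to follow-up rate of 15% has been considered". Section 9.3 defines the ITT set as randomised participants with data at baseline, 6 months and 18 months. Section 9.4.2 defines it as all randomised participants, with multiple imputation of missing 6-month data under MAR.

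**Where the outcome data come from.** Remission needs HbA1c (or fasting glucose) below a threshold plus a period off antidiabetic drugs. Of the laboratory tests, Section 8.1 says "they are part of the routine clinical practice for monitoring and follow-up of all patients with type 2 diabetes mellitus", that nothing is done outside standard care, and that the work is done at the participant's own centre. The trial already uses eCAP for recruitment, year of diagnosis and comorbidities, and as source data (10.1.8, 10.1.9.1). It also uses eCAP for hypo- and hyperglycaemia counts: "For the control group (Group B), episodes will be identified through records in the electronic health record system (eCAP)". The consent described in 8.1 covers data collection for the duration of the study.

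**The concern.** Losing telephone contact is not the same as losing the outcome when the laboratory value may already sit in a record that the trial reads. As written, the plan either drops that person (9.3) or replaces the value with a model-based one (9.4.2), without first looking for it.

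Two things are at stake. Missing outcomes reduce power for the remission comparison on which the sample size rests. They also make the answer depend on MAR, which the data cannot test. In an open-label trial it is plausible that people who vanish from follow-up did worse than those who stay.

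The data source, and consent to read records after contact is lost, must be settled before enrolment. They cannot be repaired at the analysis stage.

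**Working it through.** **Inputs (Section 9.2).** "Accepting an alpha risk of 0.05 (5%) and a beta risk of less than 0.2 in a two-sided test". Control remission: "For the control group, the expected remission rate ranges from 0 to 5" per cent. Intervention remission: at least 25%. Required: 52 per arm. Recruited: 60 per arm, 1:1. Loss: 15%, not split by cause.

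**1. The plan's own figures.**
- The usual two-proportion formula is n = [1.96·√(2p̄q̄) + 0.84·√(p₁q₁ + p₂q₂)]² / (p₂ − p₁)².
- At 5% versus 25% it gives 49 per arm, or 59 with continuity correction.
- At 2.5% versus 22.5% (midpoint of the control range, same 20-point difference) with continuity correction it gives 52. The 52 is therefore reproducible, though the documents do not say which inputs were used.
- 52 × 1.15 = 59.8, rounded to 60, which is the stated figure.
- 60 × 0.15 = 9 lost per arm (18 in all), leaving 60 × 0.85 = 51, one below the stated 52.

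**2. Power for remission, 5% versus 25%, two-sided 0.05, by exact binomial enumeration.** The share that records could recover is not in the documents. It is an assumption, shown over its whole range.

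| Recovered of 9 lost per arm | Evaluable per arm | Uncorrected chi-square | Fisher |
|---|---|---|---|
| 0 | 51 | 84.4% | 76.1% |
| 4 (about half) | 55 | 87.3% | 80.1% |
| 7 | 58 | 89.2% | 82.9% |
| 9 (all) | 60 | 89.8% | 84.5% |

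The pooled normal approximation gives 81.7% at 51 and 87.6% at 60. By any of the three methods, full recovery adds about 5 to 8 points of power.

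**3. Dependence on the missing outcomes.** Suppose 25% versus 5% is observed among those with data, a 20-point difference.
- *15% missing per arm.* Observed remitters as a share of all randomised: 0.85 × 25 = 21.25% and 0.85 × 5 = 4.25%.
  - Lower bound (missing are remitters in control only): 21.25 − (4.25 + 15) = 2 points.
  - Upper bound (missing are remitters in intervention only): (21.25 + 15) − 4.25 = 32 points.
  - All missing are non-remitters: 21.25 − 4.25 = 17 points.
- *Half recovered, 7.5% missing per arm, observed rates unchanged.* 0.925 × 25 = 23.125% and 0.925 × 5 = 4.625%.
  - Lower bound: 23.125 − (4.625 + 7.5) = 11 points.
  - Upper bound: (23.125 + 7.5) − 4.625 = 26 points.
- *All recovered.* 20 points, with no range.

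For scale, 9 unknown outcomes per arm exceed the 60 × 0.05 = 3 remissions expected among controls.

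**4. Sections 9.3 and 9.4.2 side by side.** Under 9.3, someone seen at month 6 but lost before month 18 leaves the ITT set even though the 6-month outcome was observed. Under 9.4.2 that person stays in. Both cannot define the primary set.

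**The case against.** A reader might infer from 7.3 that three unanswered calls end outcome collection. The text does not say so. Visits must also have been missed, and reminders and rescheduling are planned. The stated consequence is exclusion from the intervention; the section is silent on outcomes. People who merely stop the programme fall under 7.1, which plans continued visits if they consent. Nothing forbids using a routine HbA1c after contact is lost, and 10.1.4 says data from routine samples will be used.

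A reader might also infer that much of the 15% is avoidable. No figure supports that. The loss is not split by cause. If the study draw is itself the routine draw, missing one may mean missing the other. Recovery then needs another test near the right month, and no section says how often that happens. eCAP as the source of prescriptions is a reasonable inference from the medication review and the DDD variable, but 6.5 speaks only of recording concomitant drugs at visits. Withdrawn consent cannot be worked around.

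On size, 60 per arm was chosen to absorb this loss. At 51 per arm the chi-square and normal calculations still exceed 80%; only Fisher's test falls below, and the protocol does not plan it. Section 9.4.2 analyses HbA1c change by ANCOVA, to which two-proportion powers do not apply, and it promises sensitivity analyses under other missing-data mechanisms.

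All of this limits the claim. What stands is that no section provides the fallback, that sensitivity analyses are a weaker answer than an observed value, and that 9.3 contradicts 9.4.2.

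**Conclusion.** The point holds as a specific gap worth closing before enrolment. The protocol does not say that the outcome of a participant lost to follow-up will be taken from records. By its own description, the laboratory component is routine care and the record system is already in use. The outcome goes missing through the silence of 7.2 and 7.3 combined with 9.3 or 9.4.2, not through any instruction in 7.3 to stop collecting data.

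The benefit depends on an unknown recovery share. From 0 to 100%, evaluable patients run from 51 to 60 per arm and chi-square power from 84% to 90% (Fisher 76% to 85%). That is a modest gain, and the documents do not support saying that the trial is underpowered for this reason. The main gain is less reliance on MAR: the extreme-case range narrows from 2–32 to 11–26 points if half is recovered.

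These figures assume 5% versus 25% remission, 15% loss in each arm, and remission as the endpoint, as in Section 9.2.

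**What to change.** Add one paragraph to 7.2 and 7.3, worded for both arms:

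- Unless the participant withdraws consent to use of records, take from eCAP the HbA1c and fasting glucose nearest month 6 and month 18, within a window fixed in advance.
- Take the antidiabetic prescriptions covering the drug-free interval that the endpoint already requires, from eCAP or the linked prescription record. Name that source.
- Treat these values as observed outcomes in the analysis of all randomised participants. Flag their source, and impute only when no record exists in the window.
- Rewrite the ITT definition in 9.3 to agree with 9.4.2, so that it does not depend on having data at all three time points.

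**Cost.** A paragraph of text, a check that the information sheet covers record access after contact is lost, and a look-up for about 18 people if the 15% is right.

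**Downside.** Routine values are less exactly timed than study visits and may not be confirmed as fasting, and a prescription record does not prove what was taken. A sensitivity analysis without the record-derived outcomes would show whether this matters.

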8 STUDY ASSESSMENTS AND PROCEDURES

8.1 ENDPOINT AND OTHER NON-SAFETY ASSESSMENTS

To evaluate the effectiveness of the CREDOenAP intervention on the different health indicators defined in the objectives, various variables will be collected.

Sociodemographic Variables

- **Sex:** dichotomous variable according to biological sex (Male/Female).

- **Age:** age at study entry.
- **Living situation:** current living arrangement (Lives alone / Lives with others).
- **Socioeconomic level:** determined using the individual health insurance card (TSI) based on the pharmaceutical copayment level. Copayment is calculated according to each individual's income and employment status. Based on the copayment contribution, individuals are categorized into four socioeconomic levels:
 - **Very low:** TSI 001, exempt from copayment. Includes individuals receiving minimum insertion income, active insertion income, guaranteed citizen income, exhausted unemployment benefits, or non-contributory pensions.
 - **Low:** TSI 002 (10% copayment) and TSI 003 (40% copayment). Population with annual income < €18,000.
 - **Medium:** TSI 004 (50% copayment) and TSI 006. Population with annual income €18,000–€100,000 or individuals in administrative mutual schemes.
 - **High:** TSI 005 (60% copayment). Population with annual income > €100,000.

Clinical Variables

- **Year of T2DM diagnosis:** year of T2DM registration in eCAP.
- **Main comorbidities:** the primary active diagnoses recorded in eCAP will be obtained and corroborated with the participant.

Primary Outcome Variables

All primary outcome variables will be measured, calculated, and recorded at study baseline, at the end of the intervention, and 12 months after the intervention.

- **Presence of T2DM remission** (according to ADA consensus definition, (Riddle *et al.*, 2021)):
 - **Glycated hemoglobin (HbA1c):** T2DM remission will be considered if HbA1c is < 6.5% after 6 months of intervention and at least 3 months without antidiabetic medication. HbA1c will be determined by blood analysis after a minimum of 8 hours of fasting (Association, 2021)
 - **Fasting plasma glucose:** T2DM remission will be considered if fasting venous plasma glucose is < 126 mg/dL after 6 months of intervention and at least 3 months without antidiabetic medication. Fasting plasma glucose will be measured by venous blood analysis after a minimum of 8 hours of fasting (Association, 2021)

Secondary Outcome Variables

All secondary outcome variables will be measured, calculated, and recorded at study baseline, at the end of the intervention, and 12 months after the intervention.

a) Cardiovascular Risk Factors

- **Blood pressure:** Blood pressure will be measured three times after the participant has been seated at rest for 10 minutes with uncrossed legs. The mean of the last two measurements will be used for statistical analysis. Systolic and diastolic blood pressure will be reported in mmHg using a brachial cuff sphygmomanometer.
- **Total cholesterol:** Measured in mg/dL via blood analysis.
- **HDL cholesterol:** High-density lipoprotein (HDL) cholesterol measured in mg/dL via blood analysis.
- **LDL cholesterol:** Low-density lipoprotein (LDL) cholesterol measured in mg/dL via blood analysis.
- **Apolipoprotein B100 (ApoB100):** A protein involved in cholesterol transport and relevant for evaluating elevated cholesterol causes, measured in mg/dL via blood analysis.
- **Triglycerides:** Measured in mg/dL via blood analysis.
- **Presence and size of atherosclerotic plaques in carotid arteries:** Assessed via Carotid ultrasonography. If plaques are present, the total plaque area will be measured in cm², and changes in plaque area will be tracked throughout the study.

b) Metabolic Indicators

- **Weight:** Measured in kilograms using a calibrated scale.
- **Body Mass Index (BMI):** Calculated from weight and height using the formula: BMI = weight (kg) / [height (m)]².
- **Abdominal circumference:** Measured at the midpoint between the lowest rib and the iliac crest during maximal inspiration and expiration, in centimeters.
- **Insulin resistance:** Evaluated using the HOMA-IR index (Homeostasis Model Assessment of Insulin Resistance), which estimates insulin resistance and beta-cell function. Determined via blood analysis after a minimum 8-hour fast. Values above 2.5 may indicate T2DM. Calculated as: [fasting insulin (μU/mL) x glucemia basal (mmol/L)] / 22.5 = [fasting insulin (μU/mL) x (Glucemia basal (mg/dL) x 0,0555)] / 22.5 (*HOMA Calculator — Radcliffe Department of Medicine, n.d.*)
- **Pancreatic activity:** Assessed using the HOMA-B index, which evaluates the function and activity of pancreatic beta cells. HOMA-B, together with HOMA-IR, helps in the diagnosis of T2DM. Values between 167 and 175 are considered normal and not indicative of T2DM. Values below this range suggest impaired beta-cell function, resulting in insufficient insulin production (insulinopenia). (*HOMA Calculator — Radcliffe Department of Medicine, n.d.*)
- **Fasting insulin:** Measures the amount of insulin in a blood sample. Insulin is a hormone produced by the pancreas. Normal values range between 5–25 U/mL. It will be measured via blood analysis after a minimum 8-hour fast.
- **Metabolic Syndrome Diagnosis:** Refers to a cluster of metabolic abnormalities considered a high-risk factor for cardiovascular disease and other health complications. It will be assessed according to the criteria of the International Diabetes Federation (IDF) new classification. (*International Diabetis federation (IDF), 2006*) y National Cholesterol Education Program's Adult Treatment Panel III (NCEP ATP III) (*Alexander et al., 2003*).

Metabolic Syndrome Diagnosis is established if at least three of the following five criteria are present:

- Abdominal circumference: Men of European descent > 94 cm; Women of European descent > 80 cm. For other ethnicities, cut-off points are defined according to the International Diabetes Federation (IDF). (*López De La Torre et al., 2010*)
- Fasting glucose: > 100 mg/dL or receiving pharmacological treatment for hyperglycemia.
- Triglycerides: > 150 mg/dL or receiving lipid-lowering therapy.
- HDL cholesterol: < 40 mg/dL in men; < 50 mg/dL in women, or receiving lipid-lowering therapy.
- Blood pressure: Systolic > 130 mmHg or Diastolic > 85 mmHg, or receiving antihypertensive treatment.

- **NAFLD Liver Fat Score:** Non-alcoholic fatty liver disease (NAFLD) is a condition characterized by excessive fat accumulation in the liver. Its severity can vary according to the score: < -1.455 low risk, -1.455 to 0.675 intermediate risk, > 0.675 high risk (*Angulo et al., 2007; Kotronen et al., 2009*).

The calculation is determined using the following formula:

$$-2.89 + 1.18 \times \text{Metabolic Syndrome (Yes = 1 / No = 0)} + 0.45 \times \text{T2DM (Yes = 2 / No = 0)} + 0.15 \times \text{Fasting Insulin (mU/L)} + 0.04 \times \text{Fasting Serum AST (U/L)} - 0.94 \times \text{AST/ALT ratio}$$

- **NAFLD Fibrosis Score:** The identification and quantification of fibrosis are clinically relevant since fibrosis is associated with an unfavorable clinical prognosis. An NFS > 0.676 indicates the presence of advanced fibrosis (*Angulo et al., 2007; Kotronen et al., 2009*). The calculation is determined using the following formula:

$$-1.675 + 0.037 \times \text{Age (years)} + 0.094 \times \text{BMI (kg/m}^2\text{)} + 1.13 \times \text{IFG/diabetes (Yes = 1 / No = 0)} + 0.99 \times \text{AST/ALT ratio} - 0.013 \times \text{Platelets (\times 10}^9\text{/L)} - 0.66 \times \text{Albumin (g/dL)}$$

c) Healthy lifestyle habits

- **Physical activity:** Physical activity will be assessed using the International Physical Activity Questionnaire (IPAQ). It consists of seven questions regarding the frequency, duration, and intensity of physical activity (moderate and vigorous) performed during the previous seven days, as well as walking and sitting time on a typical workday. The questionnaire may be administered through face-to-face interview, telephone interview, or self-administered survey (*Mantilla Toloza & Gómez-Conesa, 2007*).
- **Nutritional and energy composition:** The *24-hour dietary recall questionnaire* will be administered at each biweekly visit. This questionnaire is a reference tool in most

nutritional studies (*Block, 1982; Fanelli & Stevenhagen, 1986; Gersovitz et al., 1978; Madden et al., 1976*), and will be used to determine the daily intake of each type of food (*Freedman et al., 2017*).

- **Smoking habits:** Using a study-specific questionnaire, participants will be directly asked: *Do you smoke?* (Yes/No). If the response is affirmative, participants will be asked: *How many cigarettes do you smoke per day?*
- **Alcohol consumption:** Alcohol intake will be quantified using a questionnaire combined with a standardized alcohol unit conversion calculator. Participants will be asked about their consumption of different alcoholic beverages during the previous seven days. Using the conversion calculator, the total alcohol content (in ml of pure alcohol) will be estimated to obtain the average daily alcohol intake (*Cálculo: Cuantificación Del Consumo de Alcohol - Fisterra, n.d.; Valencia-Martín et al., 2014*).
- **Circadian habits:** Using a study-specific questionnaire, participants will be directly asked: *What time did you go to bed yesterday?* and *How many hours did you sleep today?*

d) Quality of life

- **SF-36:** This is a generic scale that provides a health status profile and is applicable both to patients and to the general population. The 36 items of the instrument cover the following domains: Physical Functioning, Role Physical, Bodily Pain, General Health, Vitality, Social Functioning, Role Emotional, and Mental Health. For each domain, items are coded, aggregated, and transformed into a scale ranging from 0 (worst health status for that dimension) to 100 (best health status) (*Alonso et al., 1995*).

e) Medication consumption

- **Defined Daily Dose (DDD) by active substance:** DDDs of the active substances consumed will be classified according to ATC7. Each ATC classification has a defined daily dose based on international standards, which determine the recommended maximum daily amount for the approved indication of the active substance (*WHOCC, n.d.*).

Control variables and management of T2DM

Patients will be assessed during each follow-up telephone visit throughout the intervention, at the end of the intervention, and one year after its completion. For the control group (Group B), episodes will be identified through records in the electronic health record system (eCAP).

- **Number of hypoglycemia episodes:** Episodes of hypoglycemia detected by patients through capillary blood glucose levels and/or recorded in eCAP during the intervention (plasma glucose <60 mg/dl).
- **Number of symptomatic hyperglycemia episodes:** Episodes of hyperglycemia recorded in eCAP during the intervention (plasma glucose >350 mg/dl accompanied by compatible symptoms such as general malaise, nausea, asthenia, among others).

- **Total number of healthcare visits:** Annual contacts with the healthcare system including Primary Care (physicians and nursing), Specialized Care, and Emergency Care.
- **Number of diabetes-related emergency episodes:** Emergency visits related to diabetes during the intervention period.

Recruitment

Through the internal registry of the Primary Care Clinical Station (eCAP), patients with a diagnosis of Type 2 Diabetes Mellitus (T2DM) from each primary care center (CAP) will be identified. Potential participants will be validated by a physician not involved in the intervention, in order to exclude false positives due to registry errors and to confirm inclusion and exclusion criteria.

Randomization will be performed by stratifying according to the characteristics defined in section 6.2. Study Design.

Potential participants will receive an invitation to take part in the study during their last medical consultation (in person or by telephone) by their physician, nurse, or the principal investigator. They will then be scheduled for a screening visit with a member of the research team, following completion of the screening blood test. Patients will be informed of the necessary requirements for the laboratory tests (fasting status and first morning urine sample) as well as the location where they will be carried out (extraction and laboratory areas of each primary care center).

Screening and Study Inclusion Visit

During this visit, eligibility criteria will be assessed to determine whether patients meet the study selection requirements. Participants who fulfill the criteria will receive a detailed explanation of the study objectives and the implications of participation. They will be provided with the study information sheet and, if they agree to participate, will sign an informed consent form for data collection throughout the study. If consent is obtained, a physical examination (anthropometric measurements) will be performed, sociodemographic variables will be recorded, and participants will complete the questionnaires assessing quality of life, physical activity, nutritional status, and lifestyle habits (including substance use). Additionally, appointments will be scheduled for all participants to undergo the imaging test (Carotid ultrasonography).

Laboratory Tests

Blood and urine analyses will be performed at three different time points during the study: at baseline, at the end of the intervention, and 12 months after completion of the intervention. These analyses do not involve any additional procedures, as they are part of the routine clinical practice for monitoring and follow-up of all patients with type 2 diabetes mellitus (T2DM) in primary care. No requests, extractions, or analyses will be conducted outside of standard clinical care. The laboratory tests will include: Complete blood count, HbA1c, Creatinine, Glomerular filtration rate, GOT (AST), GPT (ALT), GGT, Ionogram, Lipid profile (Total cholesterol, HDL, LDL,

Triglycerides, Apo B100), Fasting insulin, Anti-GAD antibodies (only at baseline), Urine: sediment and albumin/creatinine ratio.

Imaging Diagnosis: Carotid ultrasonography

As part of the cardiovascular risk factor assessment, three ultrasound examinations of the carotides will be performed during the study: at baseline, at the end of the intervention, and 12 months after the completion of the intervention.

	1st Examination and Sample Collection T0 (Baseline / Start of Intervention)	Follow-up Visits	2nd Examination and Sample Collection T-6 months (End of Intervention)	3rd Examination and Sample Collection T-18 months (12 months after End of Intervention)
Questionnaires and Assessment Scales				
24-Hour Recall	X	X	X	X
SF36	X		X	X
IPAQ	X		X	X
Tobacco consumption	X	X	X	X
Alcohol consumption	X	X	X	X
Circadian cycle	X	X	X	X
Physical Examination (Anthropometric Measurements)				
Weight	X	X	X	X
Height	X			
Abdominal circumference	X	X	X	X
Blood Analysis				
Complete blood count ^a (CBC ^a)	X		X	X
C-Reactive protein ^a (CRP ^a)	X		X	X
HbA1c	X		X	X
Creatinine ^a	X		X	X
Glomerular filtration rate ^a (GFR ^a)	X		X	X
Aspartate Aminotransferase (AST)	X		X	X

Alanine Aminotransferase (ALT)	X		X	X
Gamma-Glutamyl Transferase (GGT)	X		X	X
Alkaline Phosphatase ^a (ALP ^a)	X		X	X
Amylase ^a	X		X	X
Total Blood Protein ^a	X		X	X
Electrolyte Panel ^a	X		X	X
Calcium ^a	X		X	X
Phosphate ^a	X		X	X
Lipid Profile (Total Cholesterol, HDL, LDL, Triglycerides, Apo B100)	X		X	X
Basal C-Peptide ^a	X		X	X
Anti-GAD Antibodies (GAD Ab)	X			
TSH ^a	X		X	X
Free T4 ^a (Free Thyroxine ^a)	X		X	X
CA 19.9. ^a	X		X	X
Urine Analysis				
Urine Sediment ^a	X		X	X
Albumin/Creatinine Ratio ^a	X		X	X
Imaging Test (Ultrasound)				
Carotid ultrasonography	X		X	X
Type 2 Diabetes Management and Monitoring				
Hypoglycemia episode(s)		X	x	
Hyperglycemia episode(s)		X	x	

^a Parameters to assess the participant's general health status. These parameters are included in the routine monitoring of a person with type 2 diabetes (T2DM).

^b Only in cases of a discordant relationship between HbA1c values and plasma glucose.

Examinations, laboratory tests, imaging studies, and questionnaires will be conducted at the patient's primary care center (CAP Barceloneta or CAP Larrard) by healthcare personnel (physician/nurse according to the test and training) during regular working hours. Blinding will be implemented for the evaluators, as all tests and questionnaires will be carried out by personnel not

involved in the research team and not responsible for delivering the intervention, with no knowledge of the participant's assignment to group A or B in the study.

